## **Data Analysis Plan:**

### **Aim 1**

Sample characteristics from electronic surveys will be summarized by descriptive statistics. Immediately following each focus group, a summary analysis of discussion highlights will be compiled by the moderator. Overarching themes and most informative participant commentary will be further summarized to inform sequential intervention development. Subsequently, transcripts of each session will be independently reviewed by 2 study team members for confirmation of summary analysis themes and extraction of additional emergent themes. Each will aggregate (by interview question) a synthesis of major themes of participant feedback and suggested revisions. Initial thematic analysis will incorporate codes from the Health-ITUEM. A 3rd team member will assist with discrepancy resolution to ensure consensus. Content analysis will be facilitated by QSR NVivo software, v10 (Doncaster, Victoria, Australia).

### **Aim 2**

Study measures will be summarized and compared between groups using  $\chi^2$  tests for categorical variables and 2-sample *t*-tests for continuous variables. Differences between baseline and each follow-up will be calculated for continuous measures. These differences will be examined overall and within each group, with paired *t*-tests. The average change from baseline will be compared between intervention and control groups with 2-sample *t*-tests. The distribution of categorical outcomes (eg, LS7 component category: poor, intermediate, ideal) will be compared between baseline and each follow-up with McNemar's tests. All variables will be assessed and reported by sex.

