#### **Aim 2:**

We will use a cluster RCT design to evaluate app preliminary efficacy with participants randomized into the intervention or delayed intervention (control) group. This strategy ensures that all participating churches receive the intervention as mutually-preferred by our ongoing CBPR partnership. Health assessments of LS7 measures will be conducted for both groups at baseline and 6-month follow-up.

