**Schedule of Assessments**

Data Collected	# Items	Baseline	Immediate Post-intervention	6 months
Sociodemographics				
eHealth literacy: eHEALS 	10	X		
Mobile technology use skills 	13	X		
CV health (LS7) measures				
BP	--	X		X
Fasting lipid panel	--	X		X
Fasting glucose	--	X		X
Height/weight (BMI)	--	X		X
Cigarette smoking status	--	X		X
Diet quality: Delta Nutrition Intervention FFQ 	158	X	X	X
PA patterns: International PA Questionnaire 	7	X	X	X
Feasibility measures				
App engagement	--		X	X
App usability 	20		X	X
Psychosocial measures				
Diet/PA self-efficacy 	12/12	X	X	X
Diet/PA self-regulation 	16/10	X	X	X
Diet/PA social support 	10/13	X	X	X
Religiosity/spirituality: Daily Spiritual Experiences Scale 	6	X		X
Optimism: Life Orientation Test-Revised 	6	X		X
Perceived stress: Global Perceived Stress Scale 	8	X		X

**Randomization (Figure 2).** We will use a cluster RCT design with 2 waves of implementation inclusive of 2 groups: intervention (Group 1) and delayed intervention (Group 2, control group). We will randomize clusters of churches in Rochester and MSP to receive the intervention immediately following baseline health assessments including LS7 measures (Time 1, Group 1) or at post-maintenance (Time 3, Group 2). Groups 1 and 2 will complete post-intervention assessments by electronic survey of CV health behaviors, feasibility and psychosocial measures (Times 2 and 4). Both groups will complete a second health assessment at post-maintenance (Time 3), to allow for comparison of LS7 measures between Groups 1 and 2. Times 4 through 5 are data collection points following the intervention (post-intervention and post-maintenance) for Group 2. The study statistician will randomize churches, ensuring the number of participants in Groups 1 and 2 is balanced. Churches will be told their group assignment after baseline assessments.

[figure not shown]

Figure 2. RCT with delayed intervention

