## **Power Statement:**

### **Aim 1**

**Not applicable.**

### **Aim 2**

The primary outcome will be a comparison of average change in the AHA LS7 score from baseline (Time 1) to 6-months post-intervention (Time 3) between Groups 1 and 2. Based on our prior study of 37 participants, including 5 churches, the intracluster correlation (ICC) of this outcome was near zero (<0.01), and the coefficient of variation (CoV) of church sizes was 0.38 (average number of participants/church, 10; SD 3.8; CoV 0.38). Assuming similar ICC (0.01) and slightly higher CoV (0.50) since more churches will be included in the planned study, including a total of 16 churches with an average of 10 participants/church, 80 participants/group will provide 85% power to detect a difference of 1.0 in average LS7 score change between the groups (SD 2; effect size 0.50; 5% type-I error rate). The clinical significance of this 1-unit difference in LS7 score is based on a recent meta-analysis demonstrating that each unit increase in LS7 metrics is associated with an estimated 19% and 11% reduction in CVD and all-cause mortality respectively. We will recruit 200 participants to ensure 160 completers (assuming 20% attrition rate).

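### Churches are randomised, but every between-group test treats participants as independent, so the stated 5% type-I error does not hold at the plan's own ICC

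*Combined protocol and SAP*

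**What the plan says.** The design is a cluster trial. Under Overall Strategy and Design, Aim 2: "We will use a cluster RCT design to evaluate app preliminary efficacy". The randomisation paragraph below the Schedule of Assessments says: "We will randomize clusters of churches in Rochester and MSP to receive the intervention immediately following baseline health assessments".

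The Power Statement (Aim 2) sizes the trial accordingly: "Assuming similar ICC (0.01) and slightly higher CoV (0.50) since more churches will be included in the planned study". From these inputs it concludes the following: "including a total of 16 churches with an average of 10 participants/church, 80 participants/group will provide 85% power". The target is a 1-point gap between groups in mean LS7 change, and the remaining inputs are given in brackets as "SD 2; effect size 0.50; 5% type-I error rate". The ICC is taken from a prior study of 37 participants in 5 churches.

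The Data Analysis Plan (Aim 2) is one paragraph. On the primary contrast it says: "The average change from baseline will be compared between intervention and control groups with 2-sample" t-tests. Other measures are compared between groups by chi-square tests or 2-sample t-tests. Changes from baseline are examined by paired t-tests and McNemar's tests. The paragraph has no church random effect, generalised estimating equation (GEE), cluster-robust variance, church-level summary or design-effect correction, and no other section supplies one.

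**The concern.** With about 160 completers, the planned t-test uses 158 degrees of freedom, yet only 16 units were randomised. If members of one church change more alike than members of different churches, the test's standard error is too small. Its p-values are then too small, and a significant LS7 difference could reflect which churches fell into which group. This affects the primary comparison and every other between-group test.

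Enlarging the sample for clustering protects power. It does not correct the standard error of a test that ignores clustering.

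The refined app could also raise the correlation. It adds a diet and activity goal chart by church, acknowledgement of top-ranked churches and a sharing board, all of which give members of a church a reason to change together. The documents do not quantify this.

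**Working it through.** **Inputs from the Power Statement:** 16 churches, mean size m = 10, 80 participants per group, ICC = 0.01, CoV of church size = 0.50, difference 1.0, SD 2, type-I error 5%. Assumed here: a two-sided test, since sidedness is not stated, and 8 churches per group.

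**Step 1. Reproduce the stated power.**

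- Design effect for unequal clusters: DE = 1 + [(1 + CoV²)·m − 1]·ICC = 1 + (1.25 × 10 − 1) × 0.01 = 1.115.
- Effective sample size per group: 80 / 1.115 = 71.7.
- Standard error of the difference: 2 × √(2/71.7) = 0.334.
- Power: Φ(1/0.334 − 1.96) = Φ(1.035) = 0.850, matching the stated 85%.
- Without the design effect: SE = 2 × √(2/80) = 0.316 and power = 0.885.

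The stated 85% therefore includes clustering.

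**Step 2. Type-I error of the planned test.** A t-test that ignores church understates the standard error by a factor of √DE. Its real two-sided error at nominal 5% is 2·[1 − Φ(1.96/√DE)]. At ICC 0.01, 1.96/1.056 = 1.856, which gives 6.3%.

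The simulation used 20,000 null trials per ICC, with 16 churches and gamma-distributed sizes of mean 10 and CoV 0.5.

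| ICC | DE | √DE | Type-I error, formula | Type-I error, simulation |
|---|---|---|---|---|
| 0 | 1.000 | 1.00 | 5.0% | 5.0% |
| 0.01 (plan) | 1.115 | 1.06 | 6.3% | 6.1% |
| 0.02 | 1.230 | 1.11 | 7.7% | 7.4% |
| 0.03 | 1.345 | 1.16 | 9.1% | not run |
| 0.05 | 1.575 | 1.25 | 11.8% | 11.1% |
| 0.10 | 2.150 | 1.47 | 18.1% | 17.5% |

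ICCs above 0.01 are assumptions, shown as a range. In the same simulations a t-test on unweighted church means with 14 degrees of freedom rejected in 4.6% to 5.0% of null trials.

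**Step 3. How well the prior study fixes the ICC.** Take 5 churches of 37/5 = 7.4 people each (equal sizes assumed), giving 4 and 32 degrees of freedom. For an estimated ICC between 0 and 0.01, the observed F ratio is 1 + 7.4·ICC/(1 − ICC), or 1.00 to 1.07. The upper limit for F is the observed F times the 97.5th percentile of F(32, 4), which is 8.45. The upper 95% limit for the ICC is (F_U − 1)/(F_U + 6.4). At F_U = 8.45 this is 7.45/14.85 = 0.50, and at F_U = 9.08 it is 8.08/15.48 = 0.52. The prior data exclude none of the ICCs in the table.

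**Step 4. Power of a valid analysis.** With 16 − 2 = 14 degrees of freedom, the critical value is 2.145 instead of 1.975. At ICC 0.01, with the same effective sample size and efficient weighting, power is 79.5%. Unweighted church means gave about 71% in simulation.

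**The case against.** The strongest reply is that the inflation depends on the ICC being above zero. The plan's own figures put it at or below 0.01, so the excess is between 0 and about 1.3 percentage points. The larger figures rest on ICCs the documents do not state. The effect of the app's church-level features is also unquantified: before Time 3 they act in the immediate group only, and acknowledgement comes at a post-study event. Finally, the trial is described as testing feasibility and preliminary efficacy, where a small inflation matters less than in a confirmatory trial.

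The conditionality is right, and the headline figure should be the one at ICC 0.01. It does not rescue the plan. The Power Statement declares a primary comparison with a 5% error rate and assumes an ICC at which the named test misses that rate. An ICC from 5 churches gives little reassurance. If the true ICC is near zero, a church-level term adds little variance, and the main cost is the smaller degrees of freedom.

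Two further objections stand and shape the fix. A valid analysis on 14 degrees of freedom has noticeably less than 85% power, and this should be disclosed. Moving from change scores to Time 3 LS7 adjusted for baseline is not needed to correct the clustering error; it is a separate gain in precision.

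**Conclusion.** The concern holds. The sample size accounts for church and the analysis does not. At the plan's ICC of 0.01 and CoV of 0.50, the planned primary test has a type-I error of about 6.1% to 6.3% instead of 5%. At an assumed ICC of 0.05 it is about 11% to 12%. Any positive ICC pushes the error the same way, towards false-positive findings. The figures assume a two-sided test, 8 churches per group, about 10 completers per church and a common ICC in both groups. The inflation is modest at the plan's value, but it sits in the primary comparison and could be much larger. It should be corrected before analysis.

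**What to change.** Replace the 2-sample t-test for the primary outcome with a linear mixed model that has a random intercept for church and small-sample degrees of freedom (Kenward-Roger, or between-cluster with 14). A weighted church-level analysis would also serve. Either can be applied to the change score the Power Statement defines. The better choice is to model LS7 at Time 3 on group and baseline LS7, because baseline is already collected and adjusting for it can recover some of the power lost on 14 degrees of freedom.

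For the secondary and categorical group comparisons, name mixed models or GEE with a small-sample correction. Report the observed ICC for the primary outcome.

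Restate power for the chosen model: about 79.5% at ICC 0.01 without baseline adjustment, and lower at larger ICCs.

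The cost is a change of wording in the analysis plan, slightly more analysis work, somewhat larger p-values and a lower stated power. No new data are needed.

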cookbook, cooking demos and fitness classes. We enrolled 37 participants (70% women) in the 16-week [wk] program of 8 biweekly, 90-minute education sessions at participating churches. **Key Findings:** Participants had improvements in CV health knowledge/LS7 metrics along with positive trends between self-efficacy and health behaviors. *Participant evaluations indicated a keen interest in program sustainability and dissemination through integration of mobile technology or the Internet.* **Relevance to Proposed Work:** FAITH!, with a new CV health focus was expandable to a new AA faith community and improved CV health knowledge/LS7. Participant feedback guided the intervention formatting from a face-to-face program to an app to increase its access and be less resource-intensive.

**III. Developing and testing app prototype (FAITH! App Pilot Study).** Employing a CBPR approach, we co-developed an app prototype, FAITH! App (Figure 1) focused on general CV health/wellness. It included 10 core education modules on CVD risk as a video series from health professionals and basic functionality of diet/PA self-monitoring and a sharing board. We enrolled and retained 50 participants (26 in MSP, 24 in Rochester, 70% women) into a single group, 10-wk intervention centered on the modules with adjunct live sessions (cooking demos, fitness classes, meet-the-experts forum). **Key Findings (Table 1):** Analyses revealed positive perceptions and high user-satisfaction of the FAITH! App with feedback to include individually-tailored, interpersonal features to support CV health. Participants had: high mobile technology use, high eHealth literacy and overall high CVD risk with multiple risk factors at baseline (overweight/obese, 85%; physical inactivity, 40%; hypertensive, 40%; poor diet, 30%). At 28-wks post-intervention, there were significant improvements in LS7 factors/behaviors, LS7 composite score and psychosocial variables influencing behavior change. **Relevance to Proposed Work:** It is crucial to refine and rigorously test the app as a standalone intervention with LS7, individualized/interpersonal features, building logically to the proposed study.

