#### **Aim 2: Participants**

- Men and women 18 years of age and older
- AA race/ethnicity
- Basic Internet navigation skills (at least weekly access)
- Active email address
- Ownership of smartphone (supporting iOS or Android systems)
- Minimal fruit/vegetable intake (<5 servings/day)
- No regular PA program (<30 minutes/day of moderate PA)
- Able to engage in moderate PA (such as brisk walking, dancing, aerobics, gardening, weight lifting without restrictions including physical disability, use of a wheelchair daily or serious medical condition)

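### Baseline LS7 is collected but not used as a covariate in the primary comparison: adjusting for it is a cheap gain in precision (about 22-25% of variance) if churches differ little in LS7 level, and no gain at a church-level ICC of about 0.09-0.11

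*Combined protocol and SAP*

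**What the plan says.** The Power Statement for Aim 2 makes the primary outcome the between-group comparison of average LS7 change from Time 1 to Time 3. The Data Analysis Plan for Aim 2 tests it thus: "The average change from baseline will be compared between intervention and control groups with 2-sample *t*-tests". No section plans a baseline covariate, analysis of covariance or a mixed model.

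The baseline value is available. Study Design and Methods, Aim 2, states: "Health assessments of LS7 measures will be conducted for both groups at baseline and 6-month follow-up". The Schedule of Assessments lists every LS7 component at baseline and at 6 months.

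The unit of randomisation is the church: "We will randomize clusters of churches in Rochester and MSP to receive the intervention immediately following baseline health assessments including LS7 measures". On church differences, the Power Statement says of the change outcome that "the intracluster correlation (ICC) of this outcome was near zero (<0.01"), based on 37 participants in 5 churches. It then plans on an ICC of 0.01 and a church-size CoV of 0.50, and concludes that "80 participants/group will provide 85% power to detect a difference of 1.0 in average LS7 score change between the groups", with an SD of 2. No ICC is given for LS7 level.

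**The concern.** A change score subtracts the whole of the baseline value, so it fixes the baseline slope at 1. If a participant's follow-up LS7 correlates only about 0.5 with baseline and the SDs are equal, the best individual-level slope is about 0.5. The change score then over-corrects and carries avoidable noise into the primary comparison.

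Church randomisation works the other way. A stable difference in LS7 level between churches cancels completely in a change score, but a slope near 0.5 removes only about half of it. Whether adjustment helps therefore depends on how much churches differ in LS7 level. At stake is precision on the primary comparison, at almost no cost in data.

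**Working it through.** **The plan's own figure.** Inputs from the Power Statement: 16 churches of mean size 10, CoV 0.50, change ICC 0.01, SD 2, 80 completers per group, difference 1.0. A two-sided 5% level is assumed, since the sidedness is not stated.

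- Design effect = 1 + (10 × (1 + 0.5²) − 1) × 0.01 = 1 + 11.5 × 0.01 = 1.115.
- SE of the difference = 2 × √(2 × 1.115/80) = 0.334.
- Power = Φ(1/0.334 − 1.96) = 85.0%. The stated 85% is reproduced.

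**Correlation.** Table 1 gives LS7 8.4 (2.1) at baseline (N=50) and 9.0 (2.1) at 28 weeks (N=49), P=0.05. The table does not name the test. Assume a paired t-test on 49 pairs with mean difference 0.6.

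- SD of change = 0.6 × √49/2.011 = 2.09, close to the planning SD of 2.
- r = 1 − 2.09²/(2 × 2.1²) = 0.505.
- Because the two Ns differ, 0.6 need not be the paired difference. A difference of 0.5 gives r = 0.66, and 0.7 gives r = 0.33.

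**Variance with churches.** Take baseline variance as 1 and equal SDs. For slope b, the variance of the group difference is proportional to V(b) = W(b) + 12.5 × B(b). W and B are the within- and between-church variances of follow-up − b × baseline, and 12.5 = 10 × (1 + 0.5²). The change score has b = 1. The between-church covariance is set so that the change ICC stays at 0.01. Two slopes are considered: the overall slope (b = r) and the within-church slope, towards which a model with a church term tends.

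Variance of change = 2 × (1 − 0.5053) = 0.989, so V(1) = 0.99 × 0.989 + 12.5 × 0.00989 = 1.103.

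Example 1, level ICC 0.05, overall slope:

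- Between-church covariance = 0.05 − 0.00989/2 = 0.0451; within-church covariance = 0.5053 − 0.0451 = 0.4602.
- W = 0.95 × (1 + 0.2553) − 2 × 0.5053 × 0.4602 = 0.727.
- B = 0.05 × 1.2553 − 2 × 0.5053 × 0.0451 = 0.0172.
- V = 0.727 + 12.5 × 0.0172 = 0.943; ratio 0.943/1.103 = 0.855, a cut of 14.5%.

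Example 2, level ICC 0.10, within-church slope:

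- Between-church covariance = 0.0951; within-church covariance = 0.4102; slope = 0.4102/0.90 = 0.456.
- W = 0.90 − 0.4102²/0.90 = 0.713; B = 0.0341.
- V = 0.713 + 12.5 × 0.0341 = 1.139; ratio 1.033, a loss of 3.3%.

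Power uses SE = 0.334 × √(1 − cut):

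| Level ICC (assumed) | Cut, overall slope | Cut, within-church slope | SE | Power |
|---|---|---|---|---|
| Planned change score | – | – | 0.334 | 85% |
| 0.01 | 24.7% | 24.7% | 0.290 | 93% |
| 0.02 | 22.2% | 22.1% | 0.295 | 92% |
| 0.05 | 14.5% | 13.6% | 0.309-0.310 | 90% |
| 0.10 | 1.8% | −3.3% | 0.331-0.339 | 84-86% |
| 0.15 | −11% | −24% | 0.352-0.372 | 77-81% |

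Break-even is at a level ICC of 0.107 (overall slope) or 0.091 (within-church slope).

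**Sensitivity.** At a level ICC of 0.01 the cut is (1 − r)/2: 17% at r = 0.66 and 33.5% at r = 0.33. Allowing for both rounding in Table 1 and sampling error at n = 49 widens this to about 9-51%. If the follow-up SD is 1.2 times the baseline SD, the change variance is 1 + 1.44 − 2 × 0.606 = 1.228 and the adjusted variance is 1.44 × (1 − 0.255) = 1.073. The cut is then about 13% at a level ICC of 0.01, and it is gone by about 0.05-0.06.

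**Simulation check** (16 churches, CoV 0.5, mixed model, 3,000 runs per setting). Gain from adjusting for individual baseline: 24% at level ICC 0.005, 21% at 0.02, 13% at 0.05, −2% at 0.11, −10% at 0.15. Adding the church mean of baseline changed these to 18%, 15%, 8.5%, 3% and 3%.

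**The case against.** The strongest reply is that nothing here is wrong. A change-score contrast is valid under randomisation, the trial describes its aim as feasibility and preliminary efficacy, and the power calculation is on the scale analysed. All of that stands, and it is why the point concerns efficiency only. A reader might go further and infer a biased comparison or a mistaken 85%. The documents do not support that: the contrast is unbiased and the 85% reproduces. The absence of a church term in the t-test is a separate matter, which baseline adjustment does not cure.

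The second reply is that the deciding input is missing. This also stands. A reader might take the near-zero ICC as showing that churches hardly differ in LS7 level, and so treat a gain of about a quarter as likely. That does not follow, because the ICC is for change and stable church differences cancel in change. No section favours a level ICC of 0.01 over 0.10.

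Third, the correlation is soft. It comes from a rounded P value in a "single group, 10-wk intervention centered on the modules with adjunct live sessions", and the eligibility limits on diet and physical activity may narrow the baseline spread and so raise the SD ratio. This affects the size of the gain and, through the SD ratio, the break-even point.

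Fourth, any loss need not be small: at a level ICC of 0.15 it is 11-24%.

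**Conclusion.** The point holds as a conditional improvement. The primary comparison leaves a collected baseline covariate unused. With r about 0.5, equal SDs, a change ICC of 0.01, mean church size 10 and CoV 0.5, using it would cut variance by about 22-25% if the level ICC is 0.02 or below and by about 14% at 0.05. There is no gain at about 0.09-0.11, and there is a real loss beyond. A follow-up SD larger than the baseline SD lowers both the gain and the break-even. Confidence is high in the method and moderate in the size, because the level ICC is an assumption and r is back-calculated.

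**What to change.** In the Data Analysis Plan for Aim 2:

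- Make the primary analysis the group difference in Time 3 LS7, adjusted for individual baseline LS7, in a model that accounts for churches and uses small-sample degrees of freedom.
- Treat continuous secondary outcomes measured at baseline the same way, each adjusted for its own baseline.
- Keep raw mean change by group as a descriptive summary.
- Before outcome data are seen, state whether the church mean of baseline LS7 is a second covariate. It protects against loss if churches differ widely in LS7 level, and costs a few points of gain if they do not.

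The change needs no new data, visits or participants, since a change score already requires the baseline value, and the sample size can stay. The cost is a short rewrite, one or two more parameters, and a specified clustered model in place of a t-test. The remaining downside is that adjustment can lose precision if churches differ substantially in LS7 level or if follow-up LS7 is more variable than baseline.
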